#### **9.2.12 Change from both Baselines in the SHAQ at Week 52.**

The SHAQ consists of the HAQ-DI (8 domains) and also includes a visual assessment scale (VAS) for pain and the following scleroderma-specific VASs: patient global assessment, vascular, digital ulcers, lung involvement and gastrointestinal involvement [Steen and Medsger, 1997]. The 5 scleroderma-specific VASs ask subjects how much symptoms interfere with daily activities. A visual analog scale (VAS) of 0-100 is used for each item with a one-week recall period, except for the overall global item which asks the participant to rate their condition "today". Each item is considered separately and reported individually. A composite VAS score is not created nor are the individual VAS scores incorporated into the HAQ-DI score.

Each SHAQ score with corresponding change from baseline will be summarized descriptively at each time-point by treatment group. Comparisons of each dose of HZN-825 at Week 52 for the change from baseline will be done for each VAS score and will be tested

in the same manner as that described for the primary analysis of the primary endpoint in [Section 9.1](#), but based only on observed data.

#### **9.2.13 Change from both Baseline in SScQoL scores at Week 52.**

The SScQoL is a validated tool that has 29 questions divided into 5 subscales relating to physical functioning (score range: 0 to 6), emotional functioning (0 to 13), social functioning (0 to 6), sleep (0 to 2) and pain (0 to 2), which are important disease-specific factors associated with quality of life in SSc [[Sierakowska et al., 2019](#)]. The score for each subscale is determined by summing the ‘true’ responses for the questions corresponding to the subscale, where each ‘true’ response has a score of 1. Total score is calculated accordingly. High scores indicate a greater impact of the disease.

If any question is missing, then the corresponding subscale and the total score will be missing.

Each SScQoL subscale with corresponding change from both baselines to Week 52 will be summarized descriptively at each time-point by treatment group. Comparisons of each dose of HZN-825 at Week 52 for the change from baseline to Week 52 in each subscale will be tested in the same manner as that described for the primary analysis of the primary endpoint in [Section 9.1](#), but based only on observed data.

#### **9.2.14 Change from both Baselines in SF-12 scores at Week 52.**

The SF-12 [[Ware, et al., 1996](#)] is a 12-item survey used to assess general health-related quality of life. The SF-12 items are scored to generate a physical component score (PCS) and mental component score (MCS) from the subject’s perspective [[Ware, et al, 1998](#)]. The SF-12 examines 8 domains of health outcomes, including physical functioning, role-physical, bodily pain, general health, vitality, social functioning, role-emotional and mental health.

Missing items and corresponding calculation of domain, PCS, and MCS scores will be handled according to the scoring instructions for the questionnaire.

Each domain of the SF-12, the PCS, and the MCS scores with corresponding change from both baselines will be summarized descriptively at each time-point by treatment group. Corresponding change from Week 52 summaries will also be provided. Comparisons of each dose of HZN-825 at Week 52 for the change from both baselines to Week 52 will be tested in the same manner as that described for the primary analysis of the primary endpoint in [Section 9.1](#), but based only on observed data.

### **9.2.15 Change from both Baseline in pain and pain component scale scores at Week 52.**

Subjects complete a pain questionnaire that has 3 questions regarding the severity of pain experienced during the past week due to Raynaud's, arthritis and finger ulceration and/or calcinosis. Subjects rate their pain on an 11-point scale from 0 (no pain) to 10 (the worst pain imaginable).

Missing values will not be imputed.

Each pain score and change from baseline in the pain score will be summarized for each time-point by treatment group. Comparisons of each dose of HZN-825 at Week 52 will be tested in the same manner as that described for the primary analysis of the primary endpoint in [Section 9.1](#), but based only on observed data.

### **9.2.16 Change from both Baseline in the FACIT-F score at Week 52.**

The FACIT-F is a 13-item measure that assesses self-reported fatigue and its impact upon daily activities and function. It was developed in the mid-1990s to meet a growing demand for more precise evaluation of fatigue associated with anemia in cancer patients. Subsequent to its development, it has been employed in over 150 published studies, including over 40,000 patients. Studied groups have included patients with cancer, rheumatoid arthritis, osteoarthritis, psoriatic arthritis, ankylosing spondylitis, multiple sclerosis, psoriasis and SSc. The FACIT-F is reliable and valid in subjects with SSc [[Strickland et al., 2012](#)].

Each response to the 13 items is transposed according to a reversal algorithm on the scoring sheet, the sum of the transposed items is taken and multiplied by 13. The multiplied value is then divided by the number of questions answered. This results in a fatigue subscale score ranging from 0 to 52. The higher the score, the better the quality of life (lower fatigue).

Missing items for FACIT-F score will be handled according to the instructions for the questionnaire for the calculation of the Fatigue Subscale Score.

The FACIT-F subscore and change from baseline in the FACIT-F subscore will be summarized for each time-point by treatment group. Comparisons of each dose of HZN-825 at Week 52 will be tested in the same manner as that described for the primary analysis of the primary endpoint in [Section 9.1](#), but based only on observed data.

### **9.2.17 Change from both Baselines in the mRSS at Week 52.**

The mRSS total score will be derived using the method described in [Section 9.2.6](#).

Comparisons of each dose of HZN-825 at Week 52 will be tested in the same manner as that described for the primary analysis of the primary endpoint in [Section 9.1](#), but based only on observed data.

### **9.2.18 Other efficacy endpoints change from Baselines at Week 52.**

Descriptive statistics will be used for other efficacy endpoints from both Baselines at Week 52 including lung fibrosis in subjects with suitable Baseline high-resolution computed tomography (HRCT), diffusing capacity of the lungs for carbon monoxide (DLCO), serum and plasma biomarkers associated with LPAR1 pathway, inflammation and/or fibrosis, and

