2. On Day 1 (Baseline), subjects will receive the first dose of fipaxalparant (HZN-825) in this extension trial in the clinic. All Day 1 assessments should be performed before the first dose of trial drug is administered in the clinic.
3. Performed as part of the Week 52 Visit of HZNP-HZN-825-301; if applicable, the result will be considered a Trial Baseline value for this extension trial.
4. Except when strictly unavoidable, the same person should perform the assessment at each evaluation during the trial. The mRSS assessment should be performed by a qualified Investigator (or designee).
5. The lung HRCT scan should be performed within ±2 weeks of the Week 52/PD Visit.
6. DLCO can be assessed within ±2-weeks of the Week 28 and Week 52/PD Visits.
7. Daily electronic diaries will be completed for 4 weeks starting on Day 1, 4 weeks starting at the Week 22 Visit and 4 weeks starting at the Week 46 Visit.
8. Perform for WOCBP. Serum pregnancy test at [REDACTED] (or as needed). Urine pregnancy tests should also be done every 4 weeks after Day 1, which includes both in-clinic testing at scheduled visits prior to dosing [REDACTED] and at home (also a ±7-day window) by the subject and reported to the site [REDACTED]. A urine pregnancy test will also be done at the Safety Follow-up Visit.
9. A complete physical examination, including but not limited to cardiac, pulmonary, neurologic and skin assessments, as well as directed rheumatology assessments [REDACTED]
10. Vital signs (blood pressure, heart rate, respiratory rate, temperature) will be measured at each visit.
11. Additional electrocardiograms or echocardiograms will be conducted, if clinically indicated. A standard transthoracic echocardiogram will be conducted on Day 1. However, an echocardiogram that has been performed during HZNP-HZN-825-301 and within the 3 months prior to HZNP-HZN-825-302 Day 1 can serve as the Trial Baseline echocardiogram if the subject has been clinically stable.
12. See Section 9.5.3.8 for details.
13. ESR must be processed within 1 hour of the blood draw.

14. Autoantibodies include anti-centromere antibody, anti-RNA polymerase antibody, anti-topoisomerase 1 and anti-U1 small nuclear ribonucleoprotein.
15. PK samples will be collected at each of the following visits: Day 1 (pre-dose), Week 4 (pre-dose and 2 to 4 hours post-dose) and Weeks 16, 28 and 40 (pre-dose). Note: all pre-dose samples will be collected prior to any fipaxalparant (HZN-825) administration for the day.

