## 7 Data Handling

All analyses will be based on observed data. There will be no imputations for missing data except for exploratory purposes as needed.

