#### **9.1 Primary Efficacy Endpoint Analysis**

The primary efficacy endpoint will be the change from both Baselines (Trial Baseline and HZN-825 Baseline) in FVC% predicted at Week 52.

A mixed model for repeated measures (MMRM) will be fit to the data for descriptive purposes using observed change in FVC % predicted values from all planned post-Trial Baseline assessments (Weeks 16, 28, 40 and 52). The model will include the fixed covariates factors used for stratifying randomization (use of mycophenolate mofetil [yes/no] and presence of ILD [yes/no]) in the previous trial, the treatment received in the previous trial, treatment by Visit Week and Visit Week. The Trial Baseline value will be used as a continuous covariate. An unstructured covariance matrix will be used for the primary

analysis; if the model does not converge, other covariance matrices or descriptive statistics will be considered. The least squares mean (LS mean) difference in change from Trial Baseline to Week 52 in MMRM will be estimated from this model. For subjects with missing data at 1 or more time points, the available data will be included in the analysis. A similar process for the FVC % predicted for the change from HZN-825 Baseline will also be performed.

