## 9.2 Exploratory Efficacy Endpoint Analyses

Analysis of the exploratory efficacy endpoints will be conducted in the order they are listed below for both changes from HZN-825 Baseline and Trial Baseline to Week 52 as needed.

The analysis will follow the primary analysis of the primary efficacy endpoint. The analysis will be based only on observed data.

Exploratory endpoints will be summarized at each time point. Change from HZN-825 Baseline and Trial Baseline will be evaluated separately.

### 9.2.1 Change from both Baselines in HAQ-DI at Week 52

The key exploratory efficacy endpoint is the change from both baselines in HAQ-DI.

The HAQ-DI assesses the subject's level of functional ability and includes questions of fine movements of the upper extremity, locomotor activities of the lower extremity, and activities that involved both upper and lower extremities. There are 20 questions in 8 categories of functioning including dressing, rising, eating, walking, hygiene, reach, grip, and usual activities [Cole et al., 2006]. The subject's ability to accomplish each activity in the past week is indicated as: without any difficulty, with some difficulty, with much difficulty, and unable to do. Any devices that are usually used to complete activities and any categories for which help from another person is needed are also assessed.

In addition, the subject will be asked the following anchor (additional) questions at the time points specified in Section 2.1 of the protocol:

How did your systemic sclerosis limit your daily activities in the last week?

- 0: did not limit activity
- 1: mildly limited my activity
- 2: moderately limited my activity
- 3: severely limited my activity
- 4: very severely limited my activity

How has limitation of your daily activities changed since the start of the trial?

- +3: very much less limited
- +2: much less limited
- +1: a little less limited
- 0: no change
- -1: a little more limited
- -2: much more limited
- -3: very much more limited

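### DLCO change gets descriptive statistics only, although it has the visit schedule of endpoints that get the SAP 9.1 MMRM; if worsening subjects drop out, its Week 52 mean could look too favourable

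*SAP*

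**What the plan says.** SAP 9.2 sets a general rule for exploratory endpoints: "The analysis will follow the primary analysis of the primary efficacy endpoint". Sections 9.2.1 to 9.2.5 and 9.2.9 to 9.2.17 then apply the 9.1 model to the continuous scores: HAQ-DI, MDGA, PTGA, SSPRO-18, GIT, Raynaud's, SHAQ, SScQoL, SF-12, pain, FACIT-F and mRSS.

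Section 9.2.18 treats DLCO, HRCT lung fibrosis and biomarkers differently: "Descriptive statistics will be used for other efficacy endpoints from both Baselines at Week 52". It gives no reason.

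The 9.1 model adjusts for the two randomisation strata of the previous trial (mycophenolate use and ILD), previous treatment, visit, and treatment by visit. On baseline it says "The Trial Baseline value will be used as a continuous covariate". It keeps the available visits of subjects with incomplete data, and a similar analysis is planned for change from HZN-825 Baseline. Its status is modest: "A mixed model for repeated measures (MMRM) will be fit to the data for descriptive purposes".

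SAP 7 applies to every analysis: "All analyses will be based on observed data. There will be no imputations for missing data except for exploratory purposes as needed".

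On timing, footnote 6 of protocol 2.1 states "DLCO can be assessed within ±2-weeks of the Week 28 and Week 52/PD Visits". HRCT has a single post-baseline scan, at Week 52/premature discontinuation.

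**The concern.** DLCO is the exploratory endpoint most likely to be read beside the primary one. Protocol 9.4.9 itself pairs a DLCO decline with an FVC decline in one of its criteria for clinically significant deterioration. Under the plan, the FVC estimate at Week 52 draws on all available visits and is adjusted for baseline and strata. The DLCO estimate is the plain mean of subjects who have a Week 52 value.

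The two lung-function results could then rest on different subjects and different missing-data assumptions. If subjects whose DLCO is falling are more likely to lack a Week 52 value, the descriptive mean would lean towards those who did well, and nothing in the planned output would correct for it.

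**Working it through.** **1. Does the visit schedule explain the difference?** From the protocol 2.1 schedule and the SAP analysis sections:

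| Endpoint | Post-baseline visits | SAP analysis |
|---|---|---|
| GIT, SScQoL, SF-12, pain, FACIT-F | Weeks 28, 52 | 9.1 MMRM |
| DLCO | Weeks 28, 52 | descriptive only |
| HRCT fibrosis | Week 52 | descriptive only |

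For DLCO it does not. For HRCT it partly does: with one post-baseline scan, a repeated-measures model reduces to a baseline-adjusted analysis of completers.

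**2. How large could the effect be?** The documents give no sample size, SD, effect size or dropout rate, so there is no figure of the plan to reproduce. What follows is an illustration, and every input is an assumption:
- SD of change set to 1 at both visits.
- Correlation ρ between Week 28 and Week 52 changes of 0.5 or 0.7.
- Correlation of each change with baseline of −0.2.
- Dropout d of 10%, 20% or 30%.
- Log-odds of dropout rising by 1 per SD of worsening.
- Strata not simulated.
- 400,000 simulated subjects, so at 30% dropout the simulation error is about 1/√280,000 = 0.002 SD.

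Three estimators of the mean Week 52 change were compared:
- Observed-case: mean of Y over subjects with a Week 52 value.
- Two-visit MMRM (maximum likelihood): b0 + b1·mean(baseline) + b2·m28. The b's come from regressing Week 52 change on baseline and Week 28 change in completers. The term m28 is the Week 28 mean estimated from all subjects who have that visit.
- One-visit model: regression of Week 52 change on baseline in completers, evaluated at the overall baseline mean. This is all that HRCT allows.

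Bias in SD of change (positive = too favourable), as the range over ρ and d:

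| Dropout mechanism | Observed-case | Two-visit MMRM | One-visit model |
|---|---|---|---|
| Unrelated to outcome | 0.00 | 0.00 | 0.00 |
| Driven by Week 28 change, all have Week 28 | 0.046 to 0.176 | 0.00 | 0.042 to 0.167 |
| Same, half of dropouts leave before Week 28 | 0.047 to 0.179 | 0.021 to 0.072 | 0.043 to 0.170 |
| Driven by unseen Week 52 change, all have Week 28 | 0.090 to 0.251 | 0.047 to 0.193 | 0.087 to 0.243 |
| Same, half of dropouts leave before Week 28 | 0.086 to 0.255 | 0.069 to 0.216 | 0.083 to 0.246 |

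**3. Consistency check.** When dropout depends only on the Week 28 change X, the observed-case bias equals ρ times the mean shift in X among those who stay. At d = 20% the simulated biases are 0.087 (ρ = 0.5) and 0.121 (ρ = 0.7). Dividing by ρ gives 0.174 and 0.173, the same shift, as it should be.

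**4. Extreme case.** If exactly the worst fraction d at Week 28 leave, the bias is ρ·φ(z_d)/(1 − d):
- ρ = 0.5, d = 0.1: 0.5 × 0.1755/0.9 = 0.10.
- ρ = 0.7, d = 0.3: 0.7 × 0.3477/0.7 = 0.35.

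**5. Scale.** If the SD of DLCO change were 8 to 12 points (assumed), 0.046 to 0.176 SD would be about 0.4 (0.046 × 8) to 2.1 (0.176 × 12) points.

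**6. Precision from baseline adjustment.** With equal variances at the two times and correlation r between them, the variance of a between-group difference from ANCOVA, relative to raw change, is (1 + r)/2. For r = 0.9 and 0.7 (assumed) this is 0.95 and 0.85, a reduction of 5% to 15%.

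**The case against.** The strongest reply is that 9.2.18 does what the protocol says. Protocol 9.6.3 plans descriptive summaries for all efficacy endpoints and specifies an MMRM for FVC only; the SAP's extension of the model to other scores is the addition. SAP 9 plans no formal analysis and treats between-group comparisons and p-values as descriptive. This stands: a reader might infer that 9.2.18 contradicts the protocol or undermines a conclusion of the trial, and it does neither. What remains is that the SAP, having extended the model to five endpoints with DLCO's schedule, does not say why DLCO is left out.

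Second, a reader might infer that dropout will make DLCO look too good. The documents do not support that. They give no dropout rate or pattern. Subjects who stop drug are asked to stay to Week 52, or otherwise to have the Week 52 assessments at exit, and those include DLCO. This reduces missing data by an unknown amount: SAP 7.4 maps visits by study day, so an early exit value need not count as Week 52, and the windows themselves are in the TFL shells, which are not among the documents reviewed.

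Third, Week 28 DLCO is not hidden, since SAP 9.2 has exploratory endpoints summarised at each time point. True, but the Week 52 mean still does not draw on it.

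Fourth, the MMRM also uses observed data only and is no cure. Its gain is partial follow-up under missing at random. When dropout follows unseen values, or subjects leave before Week 28, bias remains.

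**Conclusion.** The point holds for DLCO, as a minor inconsistency with a conditional consequence. The Week 52 descriptive mean uses neither baseline, strata, nor the Week 28 value of subjects without a Week 52 value, although a model that does so is already planned for endpoints on the same schedule.

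Under the assumptions above, the mean would be too favourable by about 0.05 to 0.18 SD if 10% to 30% drop out according to their Week 28 change, and by nothing if dropout is unrelated to outcome. The MMRM removes the bias in the first case when dropouts have a Week 28 value, and only part of it in the others. None of these inputs comes from the documents.

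A reader might extend the dropout argument to HRCT. It does not carry over: with one post-baseline scan, the adjusted model's bias is almost that of the plain mean (0.042 to 0.167 against 0.046 to 0.176 SD). The case for adjustment there is precision only.

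**What to change.** In SAP 9.2.18, add the 9.1 MMRM for DLCO change, using Weeks 28 and 52. Terms: baseline DLCO, ILD, mycophenolate, previous treatment group, visit and group by visit. Run it for each Baseline and report LS mean change with 95% CI by group. Keep the descriptive tables beside it, and report the number of subjects missing DLCO at Week 52. If the model is deliberately not wanted for DLCO, state the reason.

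For HRCT fibrosis, an ANCOVA on the baseline value and the same strata may be added, described as a gain in precision and not as protection against dropout. Biomarkers can stay descriptive.

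The cost is SAP wording and a further run of a model already planned for other endpoints. No new data are needed.

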## **10 Safety and Tolerability Analyses**

All safety analyses will be based on the Safety Analysis Set. All safety endpoints will be summarized using descriptive statistics for both Baselines.

### **10.1 Extent of Exposure**

Exposure to HZN-825 in HZN-825-302HZNP-HZN-825-302 will be descriptively summarized by treatment group: drug exposure, measured as duration of treatment (days treated), is the number of days on treatment based on the first and last days of treatment with the study medication (last day of study medication – first day of study medication + 1). This will be based on the trial drug dispensation CRF page.

Summary statistics will be provided for the duration of exposure to study medication (days) by treatment group. Additionally, a categorical breakdown of duration of treatment will be provided, including the following categories: 0 – 3 months, > 3 to 6 months, > 6 to 9 months, and > 9 to 12 months, > 12 to 15 months, > 15 to 18 months, > 18 to 21 months, > 21 to 24 months.

Summary statistics will also be presented for the total number of HZN-825 doses and total dose administered by treatment group.

### **10.2 Treatment Compliance**

The calculation of overall compliance is based on all doses in HZNP-HZN-825-302.

The formula for compliance (%) is calculated as: (cumulative actual dose / prescribed dose for time spent on study treatment)\*100.

The prescribed dose for time spent on study treatment is calculated as: (date of last administration – date of first administration + 1) \* daily prescribed dose.

The following summaries will be provided by treatment group:

- Summary statistics for percentage overall compliance.
- Percentage overall compliance categorized by frequencies < 70%, 70%-80%, 80%-90%, and > 90%.

A subject individual treatment compliance listing will be provided.

## **10.3 Adverse Events**

### **10.3.1 Treatment-Emergent Adverse Events.**

Treatment-emergent adverse events (TEAEs) are defined as any AEs with an onset date on or after the trial drug start date and time (if known) and no later than 28 days after permanent discontinuation of trial drug.

Refer to the table, listing, and figure shell document for determination of TEAE status in adverse events that are missing critical AE date start and stop information. All TEAEs will be evaluated for both treatment periods (start from first dose at HZNP-HZN-825-301 and HZNP-HZN-825-302 to the end of HZNP-HZN-825-302). Imputed dates are only used for classification of TEAEs.

Prior AEs are defined as any AE with a start date prior to the date of first dose of study treatment. Prior AEs will not be summarized, but will be included in listings.

Follow-up AEs are defined as any AE occurring > 28 days after permanent discontinuation of trial drug for subjects who prematurely discontinue the study medication prior to 52 weeks (i.e. 392 days after first trial drug intake). Follow-up AEs will be identified in the listings as such. Related SAEs will be followed up until resolved or until the event stabilizes and the overall clinical outcome has been ascertained.

The Verbatim terms in the eCRFs will be mapped to preferred terms (PTs) and system organ classes (SOCs) using the current version of MedDRA. Adverse events will be graded for

severity using the Rheumatology Common Toxicity Criteria (RCTC) v2.0 [[Woodworth et al., 2007](#)].

For summaries by SOC, PT, and maximum severity, a subject will only be counted once for each SOC based on the maximum severity level reported for that SOC and once for each unique PT within that SOC level at the maximum intensity level reported for that PT.

For summaries by SOC and PT only, a subject will be counted at most once at the SOC level and at most once at each unique PT within the SOC level. Summaries presenting the frequency of TEAEs by SOC and PT will be ordered alphabetically by SOC and then, within a SOC, alphabetically by PT.

Event Adjusted Incidence Rate (EAIR) is defined as number of subjects with events / total subject-years. Subject-years for each subject will be calculated as (date of first event occurred – first dose date +1)/365.25. For subjects without an event, subject-years for each subject = (last day in study – first dose date +1)/365.25.

EAIR will be summarized by SOC and PT as needed for TEAE.

Events for which the investigator did not record relationship to trial drug will be considered related to trial drug for summary purposes. However, by-subject data listings will show the relationship as missing. No imputation will be done in case of missing study treatment relationship for non-treatment emergent AEs.

The severity grade of events for which the investigator did not record severity will be categorized as “missing” for tabular summaries and data listings. The missing category will be listed last in summary presentation.

Treatment-emergent AEs will be summarized based on the Safety Analysis Set.

Summaries of the following types will be presented:

The number and percentage of subjects who experienced at least 1 TEAE will be provided and summarized by SOC, PT, and treatment group.

The following AEs summaries will be provided by SOC, PT, and treatment group. AE summaries followed by an asterisk(\*) will include the number of events and the corresponding incidence of events per PYE.:

- All TEAEs by maximum severity
- All treatment-emergent SAEs\*
- All treatment-related TEAEs\*
- All treatment-related TEAEs by maximum severity
- All treatment-related treatment-emergent SAEs
- All TEAEs meeting CRISS criteria
- All TEAEs leading to permanent withdrawal of any trial drug
- All TEAEs leading to death (ie, outcome of death)
- All follow-up adverse events
- All serious follow-up adverse events
- Subject incidence of AESIs: [REDACTED]

A brief, high-level summary of AEs described above will be provided by treatment group for the study treatment period and by the number and percentage of subjects who experienced the above AEs. All deaths observed in the trial will also be included in this summary. For the overall summary, the category of “TEAEs by maximum severity” described above will be replaced by AEs with severity > Grade 3.

The frequency of TEAEs occurring in > 5% of subjects in any treatment group will be summarized by treatment, primary SOC, and preferred term. A similar summary will be created for serious TEAEs occurring in > 3% of subjects in any treatment group by primary SOC and preferred term.

An adverse event plot will be created with AE incidences and risk differences (with corresponding exact 95% confidence interval) plotted together for the adverse events occurring in >5% of subjects in any treatment group. A similar plot will be created for SAEs occurring in > 3% of subjects in any treatment group.

In addition, data listings will be provided for the following:

- All AEs, indicating whether the event is treatment-emergent
- SAEs

- Deaths
- AEs leading to permanent withdrawal of trial drug
- Adverse events of special interest: [REDACTED]

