16. Blood samples will be collected for serum and plasma biomarkers prior to dosing on Day [REDACTED] as well as at the [REDACTED] Visit.
17. Adverse events occurring or worsening after the first dose of fipaxalparant (HZN-825) on Day 1 through the Safety Follow-up Visit will be considered treatment-emergent adverse events for this trial. All adverse events that occur from the signing of informed consent through the Safety Follow-up Visit will be recorded. The subject should be assessed for the development of new onset of scleroderma renal crisis, new onset of left ventricular failure, new onset of pulmonary arterial hypertension or right heart catheterization requiring treatment, gastrointestinal dysmotility requiring enteral (tube feeding) or parenteral nutrition or digital ischemia with gangrene, amputation or hospitalization requiring treatment.
18. Includes recording of herb/supplement use. See [Table 9.1](#) for restrictions regarding medications.

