#### **9.5.3.1.2 Documentation of Adverse Events**

AEs that are ongoing at the completion of HZNP-HZN-825-301 and/or occur prior to dosing on Day 1 will be considered pre-dose AEs. The TEAE reporting period begins with administration of the first dose of fipaxalparant (HZN-825) in this extension trial on Day 1 and continues until 4 weeks after the last dose of fipaxalparant (HZN-825) or premature discontinuation. All pre-dose AEs, TEAEs and AEs during the Follow-up Period must be recorded in the source documents and on the subject's eCRF. If a subject discontinues due to an SAE, that subject will be followed per Section [9.5.3.1.5](#).

If the Investigator observes an SAE after trial completion that he/she believes was possibly caused by fipaxalparant (HZN-825), the Investigator will report this SAE using the procedures described in Section [9.5.3.1.5](#). The Investigator is responsible for collecting and documenting the outcome of AEs/SAEs.

If specifically requested, the Investigator may need to provide additional follow-up information, such as discharge summaries, medical records, or extracts from the medical records. In this case, all subject identifiers, except for the subject number, will be blinded on the copies of the medical records before submission to the Sponsor.

Detailed information regarding all SAEs must also be recorded on the Serious Adverse Event Reporting Form. Whenever clinically appropriate, the Investigator should group together into a single term the signs and symptoms that constitute a single diagnosis. For example, cough, rhinitis and sneezing might be grouped together as “upper respiratory infection” if the Investigator is confident of the diagnosis.

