17. Adverse events occurring or worsening after the first dose of HZN-825 on Day 1 through the Safety Follow-up Visit will be considered treatment-emergent adverse events for this trial. All adverse events that occur from the signing of informed consent through the Safety Follow-up Visit will be recorded. The subject should be assessed for the development of new onset of scleroderma renal crisis, new onset of left ventricular failure, new onset of pulmonary arterial

hypertension or right heart catheterization requiring treatment, gastrointestinal dysmotility requiring enteral (tube feeding) or parenteral nutrition or digital ischemia with gangrene, amputation or hospitalization requiring treatment.

18. Includes recording of herb/supplement use. See Table 9.1 for restrictions regarding medications

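### SAP 10.3.1 defines TEAEs by onset date alone, so a carried-over AE that worsens in the extension can drop out of the 302-period summaries, contrary to the protocol and the SAP's own appendix

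*SAP*

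**What the plan says.** SAP 10.3.1 sets the analysis rule. A TEAE is "defined as any AEs with an onset date on or after the trial drug start date and time (if known"). The window closes 28 days after the drug is stopped for good. The complementary class also goes by date alone: "Prior AEs are defined as any AE with a start date prior to the date of first dose of study treatment". Its handling is explicit: "Prior AEs will not be summarized, but will be included in listings". The same section defines two windows: "All TEAEs will be evaluated for both treatment periods". One window starts at the first dose in 301 and the other at the first dose in 302; both end with 302.

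Footnote 17 of the protocol's Schedule of Assessments (Section 2.1) states a wider rule. TEAEs for this trial are "Adverse events occurring or worsening after the first dose of fipaxalparant (HZN-825) on Day 1", with a window that runs to the Safety Follow-up Visit. The SAP's appendix (Section 14) reproduces that schedule with the same rule: "Adverse events occurring or worsening after the first dose of HZN-825 on Day 1".

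Protocol 9.5.3.1.2 covers events that cross from one trial to the other: "AEs that are ongoing at the completion of HZNP-HZN-825-301 and/or occur prior to dosing on Day 1 will be considered pre-dose AEs". That section does not say what happens if such an event later worsens.

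**The concern.** Subjects roll over without a gap. Day 1 of 302 is the Week 52 visit of 301, and rollover subjects skip the 301 Safety Follow-up Visit. The protocol expects some AEs to be open on that day and classes them as pre-dose AEs. Footnote 17 is the only text that brings such an event back into the treatment-emergent count when it worsens, and SAP 10.3.1 leaves that part out.

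The primary safety objective is safety and tolerability of open-label treatment from Day 1 to 4 weeks after the last dose. Subjects who were on placebo start active drug on Day 1, and those on 300 mg QD move to 300 mg BID. An existing event that gets worse after that change is information the extension is meant to collect. If the operative definition excludes it, the summaries for the extension period understate what happened on open-label drug.

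**Working it through.** The plan gives no figure on this point and no arithmetic applies. The check applies each rule to one test case: an AE with onset in 301 after the first 301 dose, still ongoing on 302 Day 1 at Grade 1, and rising to Grade 3 after the first 302 dose. The result depends on how the worsening is recorded, so both possibilities are shown.

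| Rule | Worsening kept on the original record | Worsening entered as a new AE record |
|---|---|---|
| Protocol 2.1, footnote 17 | TEAE | TEAE |
| SAP 14, footnote 17 | TEAE | TEAE |
| SAP 10.3.1, period from first 302 dose | Prior AE: listed, contributes 0 to the summaries | TEAE |
| SAP 10.3.1, period from first 301 dose | TEAE, attributed to its 301 onset | Original event a TEAE in 301; new record a TEAE with onset in 302 |

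**Where the conflict lies.** Only the third row, original-record column, disagrees with footnote 17 on whether the event counts. The fourth row counts it but places it in 301. For a subject randomized to placebo, that onset falls on placebo.

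**Which outputs are affected.** In SAP 10.3.1 the tables by maximum severity, for treatment-emergent SAEs, for related events and for events leading to permanent withdrawal are all restricted to TEAEs. An event classed as a Prior AE is absent from each of them in the 302 period.

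**Can a version difference explain it?** No. SAP Section 3 bases the plan on Protocol Version 2.2, and the SAP's appendix reproduces the Version 2.2 schedule, which already includes worsening. Version 3.0 of the protocol has the same rule. The SAP does not present the narrower rule as a deliberate change.

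**Do the table shells fill the gap?** Not on the text available. SAP 10.3.1 refers to them for TEAE status when AE start or stop dates are missing, not for worsening.

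**How many subjects?** The documents give no AE counts, no carry-over rate and no worsening rate, so this cannot be computed.

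**The case against.** The strongest objection is that the effect depends on a recording convention. Protocol 9.5.3.1.1.1 requires an exacerbation of a chronic or intermittent pre-existing condition during a trial to be reported as an AE. An AE open at entry to 302 can reasonably be read as pre-existing for that trial. If sites enter its worsening as a new AE with its own onset date, the onset rule captures it and nothing is lost. This stands as a limit on the consequence. It does not remove the contradiction, because neither document says that a new record or onset date is created, and the eCRF completion rules are not available.

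A reader might infer that such an event is never tabulated. That goes too far, because the period starting at the first 301 dose includes it. The loss is confined to the 302-period summaries.

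Other outputs also limit the harm. SAP 10.3.1 lists all AEs with a treatment-emergent flag, lists SAEs, deaths and AEs leading to withdrawal, and includes all deaths in the overall summary. Laboratory, liver, vital-sign and ECG changes are analysed separately and do not depend on AE onset. These outputs keep the information available, but they do not put a worsened clinical event into the 302-period incidence tables.

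Finally, the protocol is not uniform. Its AE documentation section gives a TEAE reporting period without a worsening test. That section is silent on worsening and does not contradict footnote 17, so the conflict rests on the footnote and its copy in the SAP.

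**Conclusion.** The inconsistency is real and explicit. SAP 10.3.1 is narrower than footnote 17 in both documents. For the period starting at the first 302 dose, it removes a carried-over AE that worsens on open-label drug from the TEAE-based summaries, provided the worsening stays under the original onset date. In the period starting at the first 301 dose the event is counted but attributed to 301.

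Where the rule applies, it can only lower the 302-period counts. The size is unknown, and it is nil if worsening is always entered as a new record. For the proportion with at least one TEAE, a subject who has any other TEAE is counted already, so that figure moves less than the event-level and severity tables.

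Two stronger readings are tempting. One is that the loss falls mainly on subjects who had placebo in 301, because their active exposure starts on Day 1. The documents give no carry-over or worsening rates by group, so this is not supported. The other is that a co-primary safety analysis is biased. The documents state a primary safety objective served by descriptive summaries, with no formal test at stake.

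**What to change.** Amend SAP 10.3.1 as follows.

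- Define a TEAE as an AE with onset, or worsening of an AE already present, on or after the first dose of the relevant period, and apply this to each of the two periods.
- Exempt such events from Prior AE status and count them at their post-dose severity.
- State how worsening is identified: either a new AE record with its own onset date, or an increase in recorded RCTC grade. Footnote 17 gives no operational test, so this choice is for the sponsor to make and document.
- For the incidence rates per subject-year, use the date of worsening as the event date. The SAP measures time from first dose to first event, and the original onset precedes the first 302 dose.

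The cost is one or two SAP sentences and a derivation, plus a check before database lock of how the eCRF captures worsening. If grade changes are not recorded with dates, the grade-based option is not available and the new-record convention would have to be confirmed with sites.
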